# Safety Reporting

Potential Risks for Participants: loss of confidentiality, overtaxing or overburdening respondents with dementia, adverse reaction.

## **Protection Against Risks**

Loss of Confidentiality: To protect against the loss of confidentiality, a variety of safeguards are in place. First, all data obtained in research interviews is kept on secure servers and in locked cabinets at Benjamin Rose. Second, all participants are given an Identification (ID) Number; the master code sheet is kept only by the Subaward Principal Investigator ([name]) and the Research Project Coordinator ([name]). Therefore, only the PI and Project Coordinator have access to individually private information about human subjects. All data collection forms use only the ID numbers. Any electronic protected health information (ePHI) collected on human subjects is transmitted to, stored by, and accessed, via a HIPAA-compliant secure cloud provider. Such services secure the data while in transmission from the local machine to the servers and have high-level encryption in place to secure the data once it has arrived. The system ultimately chosen is certified as HIPAA-compliant has all possible modern safeguards, including but not limited to encryption, high-strength passwords, firewalls, intrusion detection, virus protection, audit trails, provision of a Business Associate Agreement (BAA), and secure off-site backup. Third, the hard copy data forms are transported from sites to Benjamin Rose in a locked briefcase or laptop case. Fourth, regarding security on the individual single board computers, all of the machines are password-protected. Antivirus, firewall, and security software are installed and regularly updated. The machines are also housed within a locking plastic case that protects them from physical attack.

Overtaxing or Overburdening Respondents with Dementia: Research interviewers are trained to use techniques and clinical procedures to avoid overtaxing or burdening respondents and to enhance communication. In past studies, we have implemented interviewing procedures specifically designed for aged and/or impaired persons. Examples include giving visual cues (choice cards), scheduling interviews at times when fatigue is less likely, and being sensitive to respondents' emotions (e.g., allowing for pauses in the interview process or taking a break so they can regain composure). Instruction in these techniques are an important part of the project's interviewer training. In addition, at the start of each interview, respondents are reminded that they are free to decline to answer any question and can end the interview whenever they choose.

Adverse Reaction: In the unlikely event that a respondent has an adverse reaction, two safeguards are in place to resolve the situation. First, the researchers involved in the study are experienced in working with this population and are prepared for coping with a respondent's emotional reactions. [name] has over 20 years of experience working directly with individuals living with dementia, as well as residential care facility staff. Second, respondents have access to the services of their referring community service agency, including experienced social workers, and are also able to receive referrals to appropriate regular communication with sites and

referring organizations to identify any problems that might arise. These procedures have been used extensively in past research.

## Adverse Event Collection and Reporting

[name] and [name] will be informed of any serious adverse events as soon as they occur and notify the Data and Safety Monitoring Team within 24 hours of notification.

In the event of an adverse event, the following information will be reviewed:

- Participant's study status.
- How the participant was recruited into the study and the efforts that took place to retain him/her.
- The nature of the adverse event and a determination of how the participant's safety has been threatened as a result.

In most mild cases (i.e., increased stress), a recommendation will be made to discontinue the individual's participation in the intervention and/or to withdraw the participant from the study. In moderate cases (i.e., unable to cope), the participant will be referred to an identified expert (the Alzheimer's Association, a geriatric care manager, or licensed clinical social worker, etc.). If the adverse event is deemed to be very serious (i.e., suicidal risk or the health/well-being of the participant is in jeopardy), the case will be reported to the appropriate authorities to intervene on the situation immediately.

Any significant adverse events will be reported to the IRB, the NIA Program Officer, and the Safety Officer within 48 hours of knowledge of occurring. A summary of all other adverse events will be reported to the NIA Program Officer and Safety Officer quarterly, unless otherwise requested.

## Potential Benefits for Participants

Increase knowledge and understanding of life story work, dementia and its consequences, and about services that might be useful now or in the future.

Enjoyment of sharing information about both positive and negative feelings related to their work, especially related to their own needs.

Enhance knowledge and theory about training residential care facility staff to implement cutting-edge life story work.

Alleviate staff burden, enhance person-centered care practices, and improve resident well-being, health and quality of life.

Data will provide both an empirical basis and practical foundation for professionals to use when working with residents with dementia from a variety of backgrounds throughout their professional caregiving career.

## Data Analysis and Coordination:

The research team and technology consultants conduct a review and thematic analysis of the data. Broadly, the analysis focuses on the feasibility of the modified LifeBio intervention as a viable solution for implementing person-centered care in residential care facilities.

In addition to monitoring fidelity, the effectiveness of the training in relation the professional staff's ability to conduct the intervention in a manner that maintains the high levels of acceptability and feasibility found in the pilot study is determined. Analysis of variance will be used to analyze responses to evaluation questions by groups (staff and residents) with respect to the program's importance and usefulness and their satisfaction. Investigators also examine whether resident outcomes (e.g., depression, anxiety, and loneliness) changed as a result of the participating in the program.

# **Retention of Study Documentation**

Per Benjamin Rose institute on Aging Policies and Procedure 800A: Client Record System, disposal of the records following a minimum of seven (7) years shall be done to ensure the confidentiality of the client and administrative records. Client and administrative records shall be burned or shredded depending on accessibility and cost of these procedures. The Sr. Vice President & COO or his/her designee is responsible for supervision of the disposal of all records.

## **Data Management**

NVivo: Focus group transcripts are loaded into NVivo, a mixed-method qualitative analysis software, for ease of analysis. A variety of tools, such as word frequency queries, text search, sentiment analysis, and coding matrices were used to validate constructs and themes that formed basis of the thematic coding structure. Them, the codes and themes from the open, inductive, and axial reads of the research team's initial readings of the project are loaded into the software and tagged line by line in a deductive approach. After transcripts are coded, the coder's project files are merged, and the team utilizes the coding comparison tool within NVivo to calculate a Cohen's Kappa Score to determine inter-rater reliability. In the event of disagreements or discrepancies between coders, the sections identified by the software are brought to the larger research group and discussed until a consensus is reached and a high level of inter-rater reliability of .85 is reached. NVivo also allows for the opinions and design preferences of existing LifeBio users, staff members, and persons living with dementia to be compared in coding matrices. The reporting of these coding matrices allows for the identification of proposed changes or recommendations for improvement.

Access Database: A database was created in access to store all project-specific documentation including referral logs, participant mailing addresses, completed screens, communication logs, survey responses.

# **Quality Control Procedures**

Standard Operating Procedures. The study's standardized operating procedures (SOP) document is located in the study's electronic record on BRIA's secure network with appropriate backup systems (filename: LifeBIO\_SBIR\_SOP.docx). [Document still in progress].

# Reports

A report was submitted to NIA on March 13, 2021 after the completion of Aim 1 A final report will be submitted upon the completion of Aim 3.

# **Data and Safety Monitoring Activities**

The Principal Investigators (PIs), [name] and [name], hold responsibility for ensuring participants' safety on a daily basis during their participation. Data and safety monitoring is assured by the study's research team senior key personnel: The subaward PI ([name]) and Project Evaluators ([name] and [name]). [name] is a licensed independent social worker (LISW), while other senior key personnel are experts in the field of dementia and comprised the study's Data and Safety Monitoring Team. This team, joined by an independent Safety Officer (SO), acts to monitor participant safety, evaluate the progress of the study, review procedures for maintaining the confidentiality of data, the quality of data collection, management, and analyses.

The PIs meet weekly with members of the research team either in-person or by teleconference to review the study's progress, review data quality, and participants' safety. At these meetings, an evaluation of the progress of the study is reviewed, including periodic assessments of data quality, timeliness of recruitment, the appropriateness of the strategies for recruiting participants into the study, assessing the participants' risk in using the LifeBio MemoryTM materials, and other factors that might have affected the study's outcomes. In addition, safety reports are sent to the SO at least twice a year and include a detailed analysis of study progress, data and safety issues.

# **Study Completion Procedures**

Successful completion of this study delivers a final LifeBio MemoryTM product that was tested by its potential customers, aimed at facilitating and enhancing communication between people living with dementia and their family and caregivers.

## Dissemination

## ClinicalTrials.gov

The Subaward Principal Investigator ([name]) ensures that processes are in place to achieve and maintain compliance with the following policy requirements for all clinical trials proposed in this application:

Clinical trial registration information is submitted to ClinicalTrials.gov no later than 21 calendar days following the study start date. Clinical trials registration initially took place for this study on 9/28/2020. The Subaward PI maintains the accuracy of the record content, resolves problems, and leads all content update and modifications within the record. Clinical trial summary results information is submitted to ClinicalTrials.gov no later than 1 year following the study completion date.

Clinical trial information submitted to ClinicalTrials.gov is verified, updated and corrected in accordance with all applicable deadlines established in the Final Rule for Clinical Trials Registration and Results Information Submission (42 CFR 11.64).

#### **Publications**

[figure not shown]
Basic results of the Aim 3 clinical trial will be reported in the ClinicalTrials.gov record within 12 months of trial completion. Research manuscripts and other publications will be submitted according to the research team's publication plan. All publications will be tracked throughout the project period and reported accordingly in annual and final project reports.

# **Appendix**

## Aim 1 Flowcharts

## Aim 1 Focus Group Study Procedures

## **LifeBio Aim 1 Focus Group Study Procedures**

## FOCUS GROUP RESEARCH OPPORTUNITY

#### ABOUT

LifeBio is a life story review program for older adults that has been used in senior living and health care organizations. LifeBio is an evidenceinformed approach that reduces loneliness while increasing social connectedness, feelings of happiness, and overall wellbeing of residents.

#### ELIGIBILITY

## Organization:

- -Familiar with the LifeBio program
  -Have purchased the LifeBio
  program in the past
- -Are currently using LifeBio within the facility or home
- -Have available staff that could participate in 2 group discussions over a 1-year period

#### Staff:

- Work at a participating independent living, assisted living, or nursing home
- Experience with dementia
- Age 18+
- Willing to contribute roughly 4 hours of their time over a 1-year period

Funded by National Institute on Agina

# WE NEED YOUR OPINION!

#### STAFF FOCUS GROUP SESSIONS

Each staff person will participate in a 2-part focus group study led by Benjamin Rose researchers. They will be asked their opinion on various LifeBio materials as well as new LifeBio Memory features.

- Part 1: A 1.5 to 2 hour virtual discussion group in November 2020.
- Part 2: A second 1.5 to 2 hour discussion group approximately 9 months later.

#### **SESSION PAYMENTS**

 Staff will received \$25 for each part they participate in. Payments will be issued by check at the end of each Focus Group part. Don't you wish you had a record of your great-grandparents' life stories? LifeBio asks a series of questions using an online template of autobiographical and biographical questions that have been carefully crafted to bring out interesting events and milestones in one's life. Topics such as family history, childhood memories, historical events, school and work experiences, early adulthood, and life lessons and beliefs are discussed and captured for generations to come to enjoy.

In this project, we are developing a new and improved product called LifeBio Memory that we will design to help you help your residents with dementia share their lives with family, staff, and others. We need your help to make this program the best it could be!

#### CONTACT US

[name]
Project Coordinator
[contact]
[contact]

To be contacted: Fill out the information below BY MONDAY, OCTOBER 12, 2020.					
Name:	Organization:				
Position:					
Email:	Phone:				
"RETURN THIS FORM TO:					

Cognitive Screen (T-MMSE)					
Now I'd like to ask you a few	questions and give you some probl	ems to solve. Pleas	e try to answer		
as best as you can.					
1. What (5)					
	WRITE DOWN RESPONSE	Incorrect	Correct		
year is this?		0 🗆	1 🗆		
season is this?		0 🗆	1 🗆		
month of the year is this?		0 🗆	1□		
is today's date?		0 🗆	1 🗆		
day of the week is this?		0 🗆	1 🗆		
2. What (4)					
	WRITE DOWN RESPONSE	Incorrect	Correct		
county are you in?		0 🗆	1 🗆		
state are we in?		0 🗆	1 🗆		
city/town are you in?		0 🗆	1□		
is the name of the		0 🗆	1□		
place/room you are in?					
them. Remember what	ee objects. After I have said all thr they are because I am going to ask " "car" "man" Please repeat t	you to name them	again in a few		
RECORD EXACT RESPONSE		0 1	2□ 3□		
NUMBER OF TRIALS		•			
SCORE ONE POINT FOR	EACH CORRECT ANSWER. IF	RESP DOES NOT	REPEAT ALL		
	HEY HAVE LEARNED ALL THE				
5 TIMES. ALLOW 20	SECONDS FOR REPLY. SCORE	E FIRST RESPONS	E ONLY.		
	LD. Now would you spell WORL	D backwards? (	5)		
D L R O W EXACT	0	1	4□ 5□		
SCORE ONE POINT FOR EA	ACH LETTER IN THE CORREC	Γ ORDER. ALLOV	V 30 SECONDS.		
5. Now what were the na	ames of the three objects that I a	sked you to remen	nber? (3)		
RECORD EXACT RESPONSE		0 1	2□ 3□		
SCORE ONE POINT FO	R EACH CORRECT ANSWER: E SECONDS.	BALL CAR MAN.	ALLOW 10		
6. Could you please tell	me what the object is you are spo	eaking into? (TELI	EPHONE) (1)		

RECORD EXACT RESPONSE			0 🗆	1 🗆
11201 01 (02		ALLOW 10 SECONDS.		
7. I'd like you to repeat	the fo	llowing phrase after me: "N	o ifs, ands, or buts.'	' (1)
RECORD EXACT RESPONSE			0 🗆	1□
		ALLOW 10 SECONDS.		
8. I'd like you to "say he	ello, ta	p the mouthpiece of the pho	one 3 times, then say	I'm back."
(3)				
FIRST COMMAND		0 🗆	1 🗆	
SECOND COMMAND		0 🗆	1 🗆	
THIRD COMMAND		$0\square$	1 🗆	
SCORE ONE POINT FOR EACH CORRECTLY PERFORMED COMMAND. ALLOW 30				
		SECONDS.		
· ·	a pho	one number where you coul	d be reached? (1)	
RECORD EXACT			0 🗆	1□
RESPONSE			 	
SCORE ONE POINT FOR A	COM	IPLETE PHONE NUMBER I	REGARDLESS OF A	CCURACY.
		TOTAL NUMBER CO	ORRECT OUT OF	26: / 26

## Abbreviations:

AE	Adverse Event
CES-D	Change in Center for Epidemiological Studies Depression Scale
CI	Confidence Interval
CMAI	Change in Cohen-Mansfield Agitation Inventory
GCDMP	Good Clinical Data Management Practices
ICI	Change in Individualized Care Instrument
IRB	Institutional review board
ITT	Intent to Treat
MMSE	Mini Mental Status Examination
PCCAT	Person-Centered Care Assessment Tool
PLWD	People (or Persons) Living with Dementia
PP	Per Protocol
SAP	Statistical Analysis Plan
SCIDS	Sense of Competence in Dementia Care Staff
SD	Standard Deviation
SPSS	Statistical Package for the Social Sciences
QoL-AD	Change in Quality of Life Alzheimer's Disease

#### 1. Administrative Information

The primary objective of this study is to assess the efficacy and safety of LifeBio Memory to increase engagement with people living with dementia and their care partners.

This document outlines the statistical methods to be implemented during the analyses of data collected within the scope of Benjamin Rose's Protocol "1908-216".

This Statistical Analysis Plan (SAP) has been developed in accordance with NIH guidance for clinical trial and behavioral research SAPs, ensuring transparency, reproducibility, and alignment with the study protocol.

## 1.1 Approvals and Oversight

- The SAP must be reviewed and approved by the following individuals prior to database lock and initiation of any analysis:
- Principal Investigator (PI) ensures alignment with study objectives and protocol.
- Sponsor/Study Funder ensures compliance with funding requirements and reporting standards.
- Lead Statistician ensures that planned analyses are appropriate, reproducible, and methodologically sound.

## 1.2 Version Control and Updates

- Any revisions to the SAP after initial approval must be documented with rationale, date, and approvers.
- Updated versions will be clearly labeled (e.g., v1.1, v2.0) and stored securely alongside previous versions.

#### 1.3 Deviations from SAP

- Any deviations from the prespecified analyses outlined in this SAP (e.g., due to unexpected missing data patterns, assumption violations, or post hoc exploratory analyses) will be documented in the final study report, including:
  - Description of the deviation
  - Reason for the deviation
  - o Date and personnel responsible for the decision
- Deviations will be reported transparently in any manuscripts or regulatory submissions to maintain integrity of the study findings.

## 1.4 Compliance with Regulatory and Institutional Policies

- This SAP, along with all associated datasets and outputs, will adhere to:
  - o Institutional review board (IRB) requirements
  - NIH/NIA policies on data management and reporting
  - Good Clinical Data Management Practices (GCDMP)

#### 2. Introduction

## 2.1 Study Background

The LifeBio Memory project is a behavioral intervention designed to enhance the well-being of residents living with dementia and to support staff in delivering person-centered care. The program uses structured life-story interviews, while providing staff with training and tools to better understand residents' preferences and histories. Previous research indicates that life-story interventions may improve quality of life, reduce depressive symptoms, and increase social engagement among persons living with dementia, while also enhancing staff competence and job satisfaction.

The current study is a non-randomized, pre-post evaluation designed to assess changes in resident and staff outcomes following participation in the LifeBio Memory program over a 4-week period. The study includes two primary participant groups: residents living with dementia and staff who facilitate/support the intervention.

## 2.2 Study Objectives

- Primary Objectives:
  - To evaluate the effect of the LifeBio Memory program on resident outcomes, including depressive symptoms (CES-D), quality of life (QoL-AD), agitation (CMAI), loneliness, and satisfaction with care.
  - To evaluate the effect on staff outcomes, including attitudes toward persons living with dementia, dementia care competence, job satisfaction, and person-centered care practices (PCCAT and ICI subscales).
- Secondary Objectives:
  - To examine changes in residents' cognitive status (MMSE) and staff knowledge of resident life stories/preferences.
  - o To assess program feasibility, training effectiveness, and satisfaction among both residents and staff.
- Exploratory Objectives:
  - To explore any potential sub-group differences (e.g., staff role, site-level differences) and consistency of outcomes across measures.

## 2.3 Purpose of the SAP

This Statistical Analysis Plan (SAP) specifies all planned analyses for the LifeBio Memory project prior to database lock and unblinding of outcome data. The SAP ensures that analyses are:

- Prespecified and reproducible, minimizing risk of bias;
- Transparent, with detailed plans for handling missing data, quality control, and statistical testing;
- Aligned with study objectives, allowing clear interpretation of primary, secondary, and exploratory outcomes.

## 2.4 Scope of the SAP

#### This SAP covers:

- Definition of analysis populations (residents and staff, ITT and complete-case).
- Data cleaning, missing data handling, and quality control procedures.
- Descriptive statistics, primary and secondary analyses, and effect size reporting.
- Subgroup and sensitivity analyses, as well as approach to multiplicity.
- Reporting conventions, including tables, figures, and adherence to the CONSORT extension for non-randomized trials.

## 3. Study Design

The LifeBio Memory project is an interventional, parallel assignment, non-randomized, open-label study evaluating the effects of a structured life-story intervention on residents living with dementia and the staff who facilitate their life story interviews.

- Participant Groups: Two primary groups will be assessed:
  - 1. Residents living with dementia participating in LifeBio Memory intervention.
  - 2. Staff who facilitate or support the intervention.
- Data Collection: Outcomes will be assessed at baseline (Time 1) and 4 weeks postintervention (Time 2). Training outcomes will be assessed immediately following the completion of intervention training videos.

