## 3.3 Randomization / Masking

 The study did not include randomization or blinding due to feasibility and practical considerations.

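### The SAP calls the study parallel assignment and sets efficacy and effect objectives, but with no unexposed comparator its paired tests can show change, not a programme effect

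*Combined protocol and SAP*

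**What the plan says.** **Design label.** SAP section 3 calls the trial an "interventional, parallel assignment, non-randomized, open-label study" and says that it evaluates the effects of the intervention. Directly below, it lists the groups: "Residents living with dementia participating in LifeBio Memory intervention" and "Staff who facilitate or support the intervention". SAP section 3.3 adds: "The study did not include randomization or blinding due to feasibility and practical considerations".

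**Competing description.** SAP section 2.1 calls the same study a "non-randomized, pre-post evaluation designed to assess changes in resident and staff outcomes".

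**Objectives.** SAP section 1 gives the primary objective as to "assess the efficacy and safety of LifeBio Memory". SAP section 2.2 sets, for residents, "To evaluate the effect of the LifeBio Memory program on resident outcomes", with a matching effect objective for staff. The protocol, under Data Analysis and Coordination, asks whether resident outcomes changed as a result of taking part.

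**Analysis.** SAP sections 5.4 and 5.5 test the primary and secondary change outcomes with paired t-tests, baseline against 4 weeks. A Wilcoxon signed-rank test is the fallback. The power statement in section 3.1 is also for paired t-tests.

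**The concern.** Parallel assignment implies two or more groups receiving different interventions and compared with each other. Here residents and staff belong to the same programme and have mostly different outcome measures, so neither can serve as the other's comparator. The label in section 3 therefore conflicts with section 2.1 and with the analysis.

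The wording of the objectives matters more. Efficacy and effect are statements about what would have happened without the programme, and nothing in the plan estimates that. A paired test responds to any systematic shift between two visits: retesting, expectation, usual care, regression to the mean, selective follow-up or the programme. Two features make this more than theoretical. Agitation (CMAI) is rated by the same unblinded staff who conduct the life story interviews (section 4.1). The main analysis population also requires a post-intervention measure (section 3.4). If the objectives stay as written, a significant paired test will appear to answer an efficacy question that it cannot answer.

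**Working it through.** **Step 1. Is there an unexposed comparator anywhere?** Each comparison in the documents, in turn:

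| Place | Comparison | Unexposed control? |
|---|---|---|
| SAP 5.4, 5.5 | Paired, baseline vs 4 weeks, within residents or within staff | No |
| SAP 5.7 | Completers vs non-completers, baseline values only | No; not a test of change |
| SAP 5.5, 5.6, 8.2 | Exploratory subgroups (site; completers vs non-completers) | No; groups defined by site or by completion, not by a planned control condition |
| Protocol, Data Analysis and Coordination | ANOVA, staff vs residents, on evaluation questions | No; both groups are in the programme |
| Protocol, Study Flow (months 16-21) | Sites start in staggered batches of three | Not used as a comparison in any analysis |

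So not every planned test is within-group, but every planned test of outcome change is paired, and none uses an unexposed control group.

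**Step 2. The plan's own power statement.** Section 3.1 gives 80% power, two-sided 0.05, for d = 0.35 to 0.40 on a paired t-test. By the noncentral t distribution this needs 67 pairs (d = 0.35) or 52 pairs (d = 0.40). At 20-25% attrition that is from 52/0.80 = 65 to 67/0.75 = 89.3, so 65 to 90 enrolled. Section 3.1 plans 160 but does not say that 160 came from this calculation. That gap is a separate matter, and this point does not depend on it. What matters here is that the stated power is power to detect change from any cause. For the analysed samples in section 3.2, at d = 0.35 to 0.40, it is 95-98% (107 residents) and 71-82% (53 staff).

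**Step 3. How often would drift alone be significant?** Assume no programme effect and a mean shift of δ, in SD units of the change score, from other causes. The documents give no value for δ, so a range is shown starting at zero. Pairs are treated as independent.

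P(p<0.05) = P(|T| > t₀.₉₇₅,ₙ₋₁), where T is noncentral t with n−1 degrees of freedom and noncentrality δ√n.

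- n = 107: critical value 1.983. At δ = 0.2, noncentrality = 0.2 × √107 = 2.069, which gives 0.536.
- n = 53: critical value 2.007. At δ = 0.2, noncentrality = 0.2 × √53 = 1.456, which gives 0.298.

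| Drift δ | 107 residents | 53 staff |
|---|---|---|
| 0 | 5% | 5% |
| 0.05 | 8% | 6.5% |
| 0.1 | 18% | 11% |
| 0.2 | 54% | 30% |
| 0.3 | 87% | 57% |

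The percentages are the same whichever way the drift runs.

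**The case against.** The SAP is open about much of this. Section 2.1 speaks of changes following participation, section 3.3 discloses the absence of randomization and blinding, and most outcomes in section 4 are titled as changes. Section 5.4 says that the primary analyses look within residents and within staff. Sections 5 and 5.6 call the work exploratory and ask for cautious interpretation, and section 5.7 goes some way towards checking for selective follow-up. The two groups are listed directly under the parallel label, so a careful reader is unlikely to imagine a control arm. The label changes no test and no sample size.

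All of that stands as mitigation, but it does not close the gap. The exploratory status is used to justify leaving out multiplicity adjustment, advanced imputation and interim analyses. It is never used to limit attribution to the programme. Section 5.6 relies on consistency across related measures, which a shared drift could also produce.

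The drift figures are hypothetical, and small drifts add little. In a progressive condition the drift could also be unfavourable, in which case it would mask benefit rather than imitate it.

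A reader might infer that the SAP claims efficacy as a finding. It does not: efficacy and effect are stated as objectives. A reader might also infer that every planned analysis is within-group; the table in Step 1 shows otherwise.

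**Conclusion.** The point holds as an error of labelling and of stated objectives. Section 3 contradicts section 2.1, and the objectives in SAP sections 1, 2.2 and 3 and in the protocol's analysis section are causal where the planned tests measure change only. This follows from the documents and needs no assumption.

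The size of the consequence does rest on assumptions: no programme effect, a drift that the documents do not give, and independent pairs. Under these, chance of significance rises from 5% with no drift to 54% (residents) and 30% (staff) at 0.2 SD.

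It would go too far to conclude that drift of that size is present, that the programme has no effect, or that the trial is invalid without a control arm. The documents contain no evidence on the first two, and a pre-post study is a legitimate design for describing change.

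**What to change.** - **SAP section 3:** replace the parallel-assignment label with *single-group, pre-post; two participant types (residents, staff)*, which agrees with section 2.1.
- **SAP sections 1, 2.2 and 3, and the protocol's Data Analysis and Coordination text:** replace the efficacy, effect and as-a-result-of wording with *change following participation*.
- **SAP section 5.4 or 5.1.7:** add *Within-group p-values test change from baseline and do not by themselves establish a programme effect.* Section 5.6 is a poorer place because it deals with multiplicity.

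The cost is wording only, with no new data, participants or analyses. The price is a less favourable claim. Section 1.2 requires a dated and approved record of the SAP change with its rationale.
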